4. STUDY DESIGN

4.1. Overall Design

This study is a Phase 2b, open-label, exploratory study of the mechanism of action of bruising and safety of CCH subcutaneously administered in subjects undergoing elective abdominoplasty surgery. Subjects will be screened for study eligibility within 28 days prior to enrolling in this 6-group, multiple dose study. Approximately 8 subjects (1 or 2 subjects per group) were originally expected to enroll and complete the study (on Day 28). An additional 2 subjects will

be enrolled to replace (for overall objective and endpoint analysis purposes) subjects whose abdominoplasty surgeries were delayed due to COVID-19 restrictions. Subjects who undergo elective abdominoplasty surgery and are willing to receive injections of CCH and have their tissue donated for evaluation (otherwise discarded post-surgery) will be eligible, provided all inclusion/exclusion criteria are met. Screening assessments and/or safety laboratory tests done within 28 days prior to (or as mandated in the protocol) the Day 1 Visit can be considered for screening purposes. In the case of subjects who have more than 28 days between initial screening and the Day 1 Visit, all screening assessments and/or safety labs will be repeated to confirm subject eligibility.

The study will be conducted in adherence to 3 main activities as follows:

1. Dosing: CCH injections as defined in this protocol
2. Abdominoplasty: Aesthetic surgery for the permanent removal/excision of abdominal tissue.
3. Histopathology and immunohistochemistry of the excised abdominal tissue.

Following a screening period of up to 28 days, subjects will be assigned to 1 of 6 groups. An additional 2 subjects will be enrolled to replace (for overall objective and endpoint analysis purposes) subjects whose abdominoplasty surgeries were delayed due to COVID-19 restrictions. Each subject will have 2 marked areas (Area 1 and Area 2) of the abdomen dosed with CCH (single or multiple doses) plus a marked non-dosed control area for comparison. The control area will be located between the 2 treatment areas. By the end of the dosing phase, Treatment Area 1 will receive a total of 2 doses (referred to as "multiple doses" in the objectives) at specified study visits for the group assigned, and Treatment Area 2 will receive a total of 1 dose (referred to as "single dose" in the objectives) at specified study visits for the group assigned. Refer to the study schema in Section 1.2 for additional details.

Subjects in each group will receive up to 3 CCH doses (each dose as either a [REDACTED] single injection technique or a [REDACTED] across 2 treatment areas at the following dosing visits:

Group 1 and Group 4 (n = 2 subjects/group): Dosing on Days -43 and -22, and -14.

Group 2 and Group 5 (n = 1 subject/group): Dosing on Days -24 and -3.

Group 3 and Group 6 (n = 1 subject/group): Dosing on Days -22 and -1.

At each dosing visit, the CCH injection dose administered per treatment area (Area 1 or Area 2) is approximately 0.07 mg CCH/0.3 mL (administered subcutaneously as 3 aliquots of [REDACTED] mL each in a single injection technique in Group 1, Group 2, and Group 3) or approximately 0.07 mg CCH/1.5 mL (administered subcutaneously as [REDACTED] of approximately [REDACTED] mL each in a [REDACTED] in Group 4, Group 5, and Group 6). Following administration of 3 doses of CCH, abdominoplasty and collection of the excised abdominal tissue will occur on Day 0. Subjects will be followed for safety until 28 days post-surgery.

The duration of the study from first subject first visit to last subject last visit will be dependent on the ability of the investigative sites to identify and enroll eligible 10 subjects. Total study duration for each subject is approximately 50 to 71 days depending on the group assigned (not including the screening period of up to 28 days). With the addition of 2 replacement subjects due

to COVID-19, the approximate duration of the study has been increased and is to be determined due to COVID-19 impacts.

4.2. Scientific Rationale for the Study Design

This is an open-label exploratory study to support ongoing clinical research of CCH in EFP.

Subjects undergoing an abdominoplasty procedure are ideal for this clinical study as it facilitates the histopathological evaluation of the excised tissue previously exposed to the investigational product via histopathology assessment.

4.3. Justification for Dose

The results from the Phase 2b study (EN3835-201) suggested that CCH 0.84 mg per treatment area (1 buttock or 1 thigh) is safe and effective. The Phase 3 studies (EN3835-302 and EN3835-303) showed a similar safety profile with most AEs being mild to moderate in severity and transient. Across all previous studies, CCH has demonstrated an acceptable safety and immunogenicity profile. In these studies, up to 12 cellulite dimples per treatment area (1 buttock or 1 thigh) were injected in each subject in one treatment session, and the approximate dose per dimple was 0.07 mg CCH. Therefore, approximately 0.07 mg per dose will be used in this study.

4.4. End of Study Definition

A subject is considered to have completed the study if the subject has completed the Day 28 post-surgical follow-up visit.

The end of the study is defined as the completion of the final assessment for the last subject enrolled in the trial.

5. SELECTION AND WITHDRAWAL OF SUBJECTS

5.1. Subject Inclusion Criteria

In order to be eligible to participate in the study, at the Screening Visit and each Dosing Visit (according to the Schedule of Activities), subjects must:

1. Be adequately informed and understand the nature and risks of the study and be able to provide consent as outlined in Section 10.1.3.
2. Be undergoing planned elective abdominoplasty.
3. Be willing to have their tissue donated for evaluation.
4. Be female and ≥ 18 years of age and ≤ 55 years of age at time of informed consent.
5. Have a body mass index (BMI) between ≥ 20.0 and ≤ 35.0 kg/m².
6. Be willing to apply sunscreen to the abdomen before each exposure to the sun while participating in the study (ie, Screening through Day 28 End of Study/Early Termination Visit).

7. Be judged to be in good health, based upon the results of a medical history, physical examination, and any standard of care laboratory profile available at Screening.
8. Be postmenopausal (of nonchildbearing potential) with no history of menstrual flow in the 12 months prior to the Screening Visit; or, if of childbearing potential, be nonpregnant, nonlactating and agree to use effective contraception when with a male partner for the duration of the study. Acceptable forms of contraception include hormonal measures (oral contraceptive pills, contraceptive patch, contraceptive ring, or injections), intrauterine devices, double barrier method (condom plus diaphragm, condom or diaphragm plus spermicidal gel or foam), surgical sterilization of the male partner, and abstinence.
9. Have a negative serum pregnancy test at screening and a negative urine pregnancy prior to the first dose of study drug.
10. Be willing and able to cooperate with the requirements of the study.

5.2. Subject Exclusion Criteria

A subject is ineligible for study participation if, at the Screening Visit and prior to injection of study drug, the subject:

1. Is from a vulnerable population, as defined by the US Code of Federal Regulations (CFR) Title 45, Part 46, Section 46.111(b) and other local and national regulations, including but not limited to, employees (temporary, part-time, full time, etc) or a family member of the research staff conducting the study, or of the sponsor, or of the contract research organization, or of the Institutional Review Board (IRB)/Independent Ethics Committee (IEC).
2. Has any of the following systemic conditions:
 - a. Coagulation disorder.
 - b. Evidence or history of malignancy (other than excised basal-cell carcinoma) unless there has been no recurrence in at least 5 years.
 - c. History of keloidal scarring or abnormal wound healing.
 - d. Concurrent diseases or conditions that might interfere with the conduct of the study, confound the interpretation of the study results, or endanger the subject's well-being. Any questions about concurrent diseases should be discussed with the Sponsor Medical Monitor.
 - e. Evidence of clinically significant abnormalities observed/recorded on physical examination, vital signs, clinical laboratory values at screening and/or during pre-surgery preparation at site (including electrocardiogram [ECG], laboratory, etc).
3. Has any of the following local conditions in the areas to be treated:
 - a. History of lower extremity thrombosis or post-thrombosis syndrome.
 - b. Vascular disorder (eg, telangiectasia) in area to be treated.
 - c. Inflammation or active infection.
 - d. Active cutaneous alteration including rash, eczema, psoriasis, or skin cancer within last 5 years.

- e. Has a tattoo and/or a mole located within 2 cm of the site of injection.
- 4. Requires the following concomitant medications before or during participation in the trial:
 - a. Anticoagulant or antiplatelet medication or has received anticoagulant or antiplatelet medication 7 days prior to injection with study drug (CCH) (except for \leq 150 mg aspirin daily, permitted only within a window-specific timeframe as determined by the investigator prior to abdominoplasty surgery).
- 5. Has history of any abdominal surgery, including but not limited to: liposuction, caesarean section, appendectomy, cholecystectomy, or umbilical hernia repair.
- 6. Has used any of the following within the timelines as identified below OR has used/intends to use any of the following:
 - a. Injections (eg, mesotherapy), radiofrequency device treatments, laser treatment, cryolipolysis, or surgery (including subcision and/or powered subcision) within the abdominal area during the 18-month period before injection of study drug.
 - b. Any investigational treatment in the abdominal area during the 12-month period before injection of study drug.
 - c. CoolSculpting® or similar treatments of the abdomen during the 18-month period before injection of study drug.
 - d. Deep massage therapy (such as Endermologie™) or similar therapy, within the abdominal area during the 6 month period before injection of study drug.
 - e. Creams (eg, Celluvera™, TriLastin®) and/or home therapies within the abdominal area during the 2-week period before injection of study drug and at any time during the course of the study.
 - f. Bath/shower salts or sugar/salt scrubs, lotions, loofahs, or other exfoliating products on the abdominal area during the 2 week period prior to injection of study drug and at any time during the course of the study.
- 7. Is presently nursing or providing breast milk in any manner.
- 8. Intends to become pregnant during the study.
- 9. Intends to initiate an intensive sport or exercise program regimen during the study.
- 10. Intends to use any tanning spray or tanning booths during the study.
- 11. Has received any investigational drug or treatment within 30 days prior to first injection of study drug.
- 12. Has a known systemic allergy to collagenase or any other excipient of study drug.
- 13. Has received any collagenase treatment at any time prior to treatment in this study.
- 14. Has a medical history of being treated with (or has received) CCH or XIAFLEX®.
- 15. Has been known to have syncope.
- 16. Any other condition(s) that, in the investigator's opinion, might indicate the subject to be unsuitable for the study.

5.3. Lifestyle Considerations

See exclusion criteria (Section 5.2).

5.4. Screen Failures

Screen failures are defined as subjects who consent to participate in this study but are not subsequently treated or who do not meet the eligibility criteria.

Subjects will be allowed to repeat any single screening assessment/procedure examination and/or vitals once, if necessary, if it is within the screening window. The subject will not be considered a screen failure unless the repeat assessment/procedure result does not meet eligibility criteria. The period from the start of screening related procedures at the Screening Visit to the first Dosing Visit must not exceed 28 days, inclusive of any repeat screening procedures. Subjects who are considered screen failures due to logistic/timing purposes surrounding the subject's availability for surgery (not including any other inclusion/exclusion criteria reasons) and/or COVID-19 restrictions, may be rescreened. Screening assessments and/or safety laboratory tests done within 28 days prior to (or as mandated in the protocol) the Day 1 Visit can be considered for screening purposes. In the case of subjects who have more than 28 days between initial screening and the Day 1 Visit, all screening assessments and/or safety labs will be repeated to confirm subject eligibility.

Subjects who do not meet all of the eligibility criteria at the Screening or first Dosing Visit will be deemed a screen failure and the following information must be recorded for all subjects who are screen failures:

- Demography (age, gender, race/ethnicity).
- Reason for screen failure.
- Which eligibility criterion was not met.
- Any AE or serious adverse event (SAE) experienced by the subject.

6. STUDY TREATMENT

Study treatment is defined as any investigational treatment, marketed products, placebo, or device intended to be administered to a study subject according to the study protocol.

6.1. Selecting and Marking Treatment Area

Each subject will have 2 marked areas (Area 1 and Area 2) of the abdomen selected for injection with CCH plus a marked non-injected control area for comparison (Figure 2). The control area will be located between the two treatment areas. Treatment areas of each subject group will be marked: Treatment Area 1 and Treatment Area 2 with the noninjected area marked as Control.

At each dosing visit, the treatment areas of each selected subject will be photographed **after marking the treatment area and the injection site with a surgical marker and a temporary tattoo (but prior to CCH dosing or the abdominoplasty procedure)**, while the subject is in a consistent, standardized relaxed standing pose. On Day of Surgery (Day 0), prior to abdominoplasty procedure, the borders of the treatment area will be marked with a surgical

marker. Following marking, the treatment areas will then be photographed while the subject is in a standing pose (as previously described). Additional instructions will be provided in the Clinical Operations Manual.

Figure 2: Diagram of Treatment Areas

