2.3. Study Rationale

CCH dose administration in buttocks or thighs with cellulite has shown to deliver an aesthetic improvement in the treated area. Endo studied the safety and efficacy of CCH 0.84 mg dose per treatment area (1 buttock or 1 thigh) in multiple Phase 2 and Phase 3 studies. In these studies, up to 12 cellulite dimples per treatment area (1 buttock or 1 thigh) were injected in each subject in 1 treatment session, and the approximate dose per dimple was 0.07 mg CCH. The efficacy results from these studies, based on improvement in cellulite severity as determined by the investigator and the subject, have consistently shown that CCH 0.84 mg dose per treatment area is an effective treatment for cellulite in buttocks or thighs. In addition, the safety and immunogenicity profile of CCH has been consistent across all these studies.

The majority of adverse events (AEs) occurred at the site of injection and resolved before the next scheduled treatment in these studies. Among the injection site reactions observed across these studies, the most common was injection site bruising. Injection site bruising observed in the clinical studies was self-limiting and predominately mild-to-moderate in severity. However, there was no histopathology examination of the injection site bruise area.

Tissue samples isolated from subjects undergoing an elective abdominoplasty procedure offer an opportunity to observe histopathological structure changes of tissues post treatment with CCH.

The histostain or microscopic examination of biological tissues may reveal the appearance of tissues in greater detail and bring better understanding of CCH treatment effect on tissue structure.

This study (EN3835-213) is an exploratory investigation to learn and compare the histopathology and immunohistochemistry changes, if any, in the subcutaneous tissue and surrounding area after single and multiple CCH injections of the abdomen across different time points. The abdominal area injected with CCH will be within the area targeted for excision during abdominoplasty.

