3. OBJECTIVES AND ENDPOINTS

Objectives	Endpoints

Primary
 
 To evaluate the histopathology and immunohistochemistry of subcutaneous tissue isolated after single and multiple CCH doses with both a [REDACTED] single injection technique and [REDACTED] (relative to control, non-dosed tissue) in adult female subjects undergoing abdominoplasty. 	
 The primary endpoint will be the change in histopathology and immunohistochemistry of tissue dosed with CCH relative to control tissue (tissue not dosed with CCH). 
 ○ [REDACTED] single injection technique: 
 ▪ Area 1 tissue relative to control for all groups. ▪ Area 2 tissue relative to control for all groups. ○ [REDACTED] 
 ▪ Area 1 tissue relative to control for all groups. ▪ Area 2 tissue relative to control for all groups.

Secondary
 
 To compare the histopathology and immunohistochemistry of tissue from treatment areas dosed with CCH in adult women undergoing elective abdominoplasty surgery. 
 ○ Multiple doses versus single dose with a [REDACTED] single injection technique. 	
 The change in histopathology and immunohistochemistry of tissue samples dosed with CCH multiple times relative to tissues dosed with CCH a single time with a [REDACTED] injection technique. 
 ○ Area 1 tissues relative to Area 2 for all groups.

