
 ○ Multiple doses versus single dose with a [REDACTED] [REDACTED] ○ Multiple doses with a [REDACTED] versus multiple dose with a single injection technique. ○ Single dosing with a [REDACTED] versus single dosing with a [REDACTED] single injection technique. 	
 ● The change in histopathology and immunohistochemistry of tissue samples dosed with CCH multiple times relative to tissue dosed with CCH a single time with a [REDACTED] injection technique. 
 ○ Area 1 tissues relative to Area 2 for all groups. ● The change in histopathology and immunohistochemistry of tissue samples dosed with CCH multiple times with a [REDACTED] single injection technique relative to tissues dosed with CCH multiple times with a [REDACTED] technique. ● The change in histopathology and immunohistochemistry of tissue samples dosed with CCH a single time with a [REDACTED] single injection technique relative to tissues dosed with CCH a single time with a [REDACTED] technique.

 ● To assess the safety and immunogenicity of CCH injected in adult women undergoing an elective abdominoplasty surgery. 	
 ● Treatment-emergent adverse events (TEAEs). ● Adverse events of special interest (AESI). ● Anti-AUX-I antibodies, anti-AUX-II antibodies, and neutralizing antibodies analysis.

The primary objective will be met if histopathology and immunohistochemistry findings in the excised abdominal tissues dosed with CCH demonstrate change from histopathology and immunohistochemistry findings in non-dosed control tissue.

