8.2.7. Adverse Events of Special Interest

AESIs for this study include:

- Bruising, ecchymosis, hematomas, and contusions that occur remote to the site of drug administration.
- Any hypersensitivity reactions, including anaphylaxis.
- Local AEs associated with the injection site, including bruising, pain, nodules/mass, ulceration, erythema, pruritus, swelling, and/or induration.

These events will be reported as AEs in the eCRF. All AEs will be evaluated for seriousness and severity. If any of these events meet the criteria for an SAE, they will also be reported as such using the procedure outlined in Section 10.3.

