9.3.1. Histopathology and Immunohistochemistry

Histopathology and immunohistochemistry findings in the excised abdominal tissues injected with CCH will be compared to histopathology and immunohistochemistry findings in non-injected control tissue. Also, histopathology and immunohistochemistry findings in the excised abdominal tissues dosed twice with CCH will be compared to histopathology and immunohistochemistry findings in excised abdominal tissues dosed only once with CCH.

The pathologist, blind to the dosing schedule, will report any observed tissue differences from the control area (not injected).

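### The only control lies between the two injected areas and the reading rule is worded as differences from it, so spread of CCH effect could mask change in both dosed areas

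*Protocol*

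**What the plan says.** Each subject has two injected areas and one control. On position, Protocol 6.1 states: "The control area will be located between the two treatment areas". The Synopsis, Protocol 4.1 and SAP 3.1 and 3.3 agree.

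The primary endpoint in Protocol 3 takes this tissue as its reference, and the objective is met if dosed tissue findings "demonstrate change from histopathology and immunohistochemistry findings in non-dosed control tissue". No second reference is described: no remote tissue, no vehicle-injected area, no pre-dose sample.

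On reading, Protocol 9.3.1 says that the blinded pathologist "will report any observed tissue differences from the control area (not injected". Protocol 6.4 and 8.1.7 and SAP 3.6 word the duty in the same way. Protocol 9.3.1 also says: "Histopathology and immunohistochemistry findings in the excised abdominal tissues injected with CCH will be compared to histopathology and immunohistochemistry findings in non-injected control tissue". The same section and SAP 3.7 plan a direct comparison of twice-dosed with once-dosed tissue.

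Two other passages bear on spread. The rationale in Protocol 2.3 covers "histopathology and immunohistochemistry changes, if any, in the subcutaneous tissue and surrounding area after single and multiple CCH injections". Protocol 8.2.7 lists among the events of special interest "Bruising, ecchymosis, hematomas, and contusions that occur remote to the site of drug administration".

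**The concern.** The study asks how bruising arises and includes tissue around the injection among its questions. Its only reference tissue lies in the ground between two injection sites. If blood or enzyme effect reaches that tissue, the control carries part of the change it is meant to exclude.

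A report written as differences would then show less change than occurred in Area 1 and in Area 2, or none. The primary success criterion does not separate true absence of change from an affected control. No later analysis is planned that would separate them: Protocol 9.3 and SAP 6 plan only subject narratives built on the pathology reports and safety listings, and SAP 7 has no dedicated histopathology display. The pathologist's wording is in effect the primary data.

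**Working it through.** **1. Head count.** Group sizes in Protocol 4.1 are 2, 1, 1, 2, 1, 1. The sum is 8, and 8 + 2 replacements = 10, which matches Protocol 9.1. With two dosed areas each, 8 × 2 = 16 dosed-versus-control contrasts. No alpha, power or effect size is stated, so there is no power figure to reproduce.

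**2. Effect of a shared, affected control.** This is an illustration in arbitrary units, since the real reading is qualitative. Assume a true change of 2 in Area 1 and 1 in Area 2, and let the control carry a share *s* of the Area 2 change. Reported change = dosed area − control, with control = *s* × 1.

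| *s* | Area 1 − control | Area 2 − control | Area 1 − Area 2 |
|---|---|---|---|
| 0 | 2 | 1 | 1 |
| 0.25 | 1.75 | 0.75 | 1 |
| 0.5 | 1.5 | 0.5 | 1 |
| 1 | 1 | 0 | 1 |

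Both primary contrasts shrink. At *s* = 0.5 the loss is 0.5/2 = 25% in Area 1 and 0.5/1 = 50% in Area 2. Only at *s* = 1 does Area 2 vanish. The comparison between the two dosed areas is unchanged throughout, because the shared control cancels.

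**3. Comparison of techniques.** Groups 4 to 6 receive 1.4 mL per dose (Protocol Table 1) or 1.5 mL (text of 6.2), against 0.3 mL in Groups 1 to 3. The ratio is 1.4/0.3 = 4.7 or 1.5/0.3 = 5. Whether volume alters spread is not in the documents. If it did, a technique contrast built from control-referenced reports would shift. With an equal true change of 1 and assumed spread of 0 against 0.25, the contrast is (1 − 0.25) − (1 − 0) = −0.25, where the true value is 0.

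**4. Reach of one affected control.** One control serves two contrasts, so *k* affected controls touch 2*k* of 16. If *k* were 1 to 3, that would be 2/16 = 12.5% to 6/16 = 37.5%. The range for *k* is an assumption, and the result is a ceiling on masking, since partial spread weakens a contrast without erasing it. In Groups 2, 3, 5 and 6 (one subject each), one affected control touches all of the group's primary contrasts. In those groups Area 1 has two doses over two sessions, so its last injection is nominally 3 days or 1 day before excision.

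**5. Safeguards in the visible text.** There is no minimum separation, no rule on where in the control the block is taken, no required description of the control by itself, and no rule for a control that shows change.

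**The case against.** The strongest reply is that the protocol does bring control findings into the comparison. Protocol 9.3.1 sets findings in injected tissue against findings in control tissue, and Protocol 9.2 requires a histopathology and an immunohistochemistry report for each evaluable subject. A reader might infer from the reading rule that differences are all the pathologist will report and that change in the control would never be recorded. The documents do not support that. Control findings are an input and may well be written down. What stands is that no visible passage requires it, while the difference wording appears four times.

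Other records could also show spread. Treatment and control areas are both marked before photographs (Schedule of Activities), and bruising at or away from the injection site is an event of special interest that SAP 7.9.2 lists. This helps with visible bruising. It does not settle microscopic change in subcutaneous tissue.

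A reader might also infer that the Area 1 versus Area 2 comparison is compromised. It is not: it is planned directly, and a shared control cancels in it.

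Spread itself is a possibility only. Protocol 2.3 speaks of changes that may or may not occur, and 8.2.7 is a clinical event definition. Layout is in Figure 2, and handling instructions are in the Clinical Operations and Histopathology Manuals, none of which could be read; a distance or reading form may be there. Finally, a control within the same excised tissue is a defensible choice for an exploratory study without hypothesis tests. All of this limits the point; none of it supplies the missing reading rule.

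**Conclusion.** The concern holds in a limited form. The sole reference for the primary endpoint lies between the injected areas, and the stated reading rule does not guarantee that an affected control would be recognised. If the control carried change of the same kind as the dosed tissue, the error would run toward no change: it could hide a primary finding but would not create one.

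The size cannot be given. It depends on the probability and degree of spread, which the documents do not state. The percentages above follow from assumed inputs and should not be read as estimates. A reader might infer that every primary contrast is biased; that would require spread in every subject, which nothing in the documents shows.

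This is a worthwhile, inexpensive improvement to the plan. It is not evidence that the design fails.

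**What to change.** In Protocol 6.4, 8.1.7 and 9.3.1 and SAP 3.6 and 3.7:

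- Have the same blinded pathologist first describe Area 1, Area 2 and control, each in its own right, on one common feature list that includes an entry for absent. Derive the contrasts afterwards.
- For subjects not yet operated on, take the control block as far as possible from both injection sites and record the distances.
- Where the control shows hemorrhage or collagen disruption, flag it in the narrative and do not count a finding of no difference in that subject as evidence of no change. Keep contrasts in which dosed tissue still clearly differs; discarding them would empty groups of one subject for no gain.
- Re-tabulate the 6 subjects who had completed surgery (Protocol 2.1) only if their reports or slides allow. Storage time is set in a manual not seen here, and block positions may not be recoverable.
- If Figure 2 or a manual already fixes the separation or the reading form, a cross-reference is enough for that part.

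The cost is a short reading form and slightly longer pathology reports. Dosing, surgery and the number of subjects are unaffected.
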